	
 • Hypersensitivity to the active substance or to any of the excipients. • Inability to provide a valid informed consent. 															
Study treatment and response criteria	DFX FCT 3.5 mg/kg. Response criteria: prevention of iron overload as measured by liver iron concentration (MRI).															
Assessments schedule	MONTHLY															
Centralized analyses	
  
 TEST	REQUIRED	QUANTITY	
   
 NTBI, LPI, Epcidine, MDA	YES see schedule	7	
 
 Serum transferrin receptor, GDF11 e 15, Erythroferrone.	YES see schedule	5	
 
 NGS (molecular tumor analysis)	YES see schedule	2	
 
 MRI liver scan	YES Baseline and EOS	2	
  
	TEST	REQUIRED	QUANTITY	NTBI, LPI, Epcidine, MDA	YES see schedule	7	Serum transferrin receptor, GDF11 e 15, Erythroferrone.	YES see schedule	5	NGS (molecular tumor analysis)	YES see schedule	2	MRI liver scan	YES Baseline and EOS	2
TEST	REQUIRED	QUANTITY														
NTBI, LPI, Epcidine, MDA	YES see schedule	7														
Serum transferrin receptor, GDF11 e 15, Erythroferrone.	YES see schedule	5														
NGS (molecular tumor analysis)	YES see schedule	2														
MRI liver scan	YES Baseline and EOS	2														
Statistical considerations	
t tests - Means: Difference between two dependent means (matched pairs) Tail(s) = Two. α err prob = 0.05
 
Effect size dz
 
 —♦— = 0.5 —○— = 0.3 
Including 50 subjects in the study, we can reach almost 60% power to detect small effect size 0.30 (with p-value of 0.05) whereas, we have almost 100% to detect moderate effect size of 0.50 (with p-value of 0.05). On the basis of previous experience, the low dosage, the early intervention and the FCT preparation a 20% drop out rate is expected (10 additional patients to be enrolled) Methods: The power test was performed by G power 3.1 software by using the t test Means: Difference between two dependent means (matched pairs). As demonstrated by our sample size analyses, we have enough power to detect an effect size between 0.3 and 0.5 considering a potential error of 0.05 which is largely accepted from scientific community.
															

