20.2. Sample size calculation

Including 50 subjects in the study, we can reach almost 60% power to detect small effect size 0.30 (with p value of 0.05) whereas, we have almost 100% to detect moderate effect size of 0.50 (with p-value of 0.05). On the basis of previous experience, the low dosage, the early intervention and the FCT preparation a 20% drop out rate is expected (10 additional patients to be enrolled)

Methods:

The power test was performed by G power 3.1 software by using the t test Means: Difference between two dependent means (matched pairs).

As demonstrated by our sample size analyses, we have enough power to detect an effect size between 0.3 and 0.5 considering a potential error of 0.05, which is largely accepted from scientific community.

The effect size is calculated on a common scale by G-power program which allows to compare the effectiveness of different variables on the same outcome. In other words, quantifies the magnitude of the difference of a variable between two population groups.

To interpret the resulting number, most scientists use this general guide developed by Cohen:

- < 0.1 = trivial effect
- $0.1 - 0.3$ = small effect
- $0.3 - 0.5$ = moderate effect
- > 0.5 = large difference effect

20.3. Statistical method and data analyses.

Analysis population: the planned enrolment target is 50 patients (+ 20% drop out rate) for a total number of 60 patients.

Data from all centers participating in this study will be pooled for analyses.

Standard descriptive analyses will include:

- Frequencies and percentages for categorical data;
- n, mean, standard deviation, minimum, median, 25th and 75th percentiles and maximum for continuous data.

Whenever possible, the analysis will be performed by visit.

Analysis sets

Full Analysis Set (FAS): All enrolled patients.

Safety analysis set (SS): All enrolled patients who will have received at least one dose of study drug and have at least one post-baseline safety assessment. Note that an entry on the Adverse Event CRF of a statement that a patient had no adverse events constitutes a safety assessment.

Per Protocol analysis set (PP): All enrolled patients who will have received at least one dose of study drug without any major protocol violations and complete the treatment study phase or withdraw from the study due to unsatisfactory therapeutic effect.

Patient demographics/other baseline characteristics

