Demographic and other baseline data (including disease characteristics and transfusion history, etc) will be summarized descriptively for the Safety analysis set by means of the statistics above mentioned. Summary tables will be provided about medical history coded by System Organ Class and Preferred Term of MedDRA dictionary.

Treatments (study treatment, concomitant therapies, compliance)

The descriptive analysis listed below will be reported for the safety analysis set.

Study drug

The duration of study drug exposure, as well as average prescribed doses, will be summarized. Any dose adjustments and reasons that led to the adjustments will be listed. The number and duration of dose interruptions will also be described.

Compliance

Compliance based on prescribed amount of study medication versus amount of medication taken based on dispensed and returned amount of study medication will be summarized.

Concomitant Therapies

Concomitant medications and significant non-drug therapies prior to and after the start of the study treatment will be coded by WHO Drug Reference List dictionary and frequencies will be calculated according to drug classes.

The primary objective is prevention of iron accumulation measured by (primary variable) Change of hepatic iron from baseline according to baseline hepatic iron level: Baseline versus end of study.

For patients with baseline LIC ≤ 5 mg/g dry weight (dw) ± 1.5 mg/g dw.

For patients with baseline LIC > 5 mg/g dw $\pm 20\%$ (by R2- MRI ; test performed in a 1.5 tesla MRI machine and analyzed following R2 method (75).

The corresponding secondary efficacy variable will be the absolute change in hepatic iron concentration EOS versus baseline.

Difference between baseline versus EOT will be measured as continuous variables and analyzed with parametric or non parametric statistical tests depending by normality of distribution.

Secondary endpoint:

Observational: demographics and other baseline characteristics will be study with descriptive statistics. Analysis will be done on FAS and PP.

As the same way secondary endpoints will be evaluated as continuous or nominal variables and analyzed accordingly with parametric or non parametric tests. Efficacy parameters analysis will be done on FAS and PP.

Final Safety parameters will be measured in full analyses set and in all patients who received at least one dose of study drug (safety set).

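### The primary endpoint sets limits on liver iron change (±1.5 mg/g or ±20%), but the planned test and the sample size address a difference from zero and never use the limits

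*Combined protocol and SAP*

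**What the plan says.** The primary endpoint is given in the synopsis, in section 17.2.1 and again in section 20.3. Section 20.3 puts it this way: "The primary objective is prevention of iron accumulation measured by (primary variable) Change of hepatic iron from baseline according to baseline hepatic iron level". Each time the limits follow: ±1.5 mg/g dw for patients with baseline LIC at most 5 mg/g dw, and ±20% for patients above 5. Each time a different quantity is then named as secondary: "The corresponding secondary efficacy variable will be the absolute change in hepatic iron concentration EOS versus baseline". The synopsis also lists LIC as the response measure: "Response criteria: prevention of iron overload as measured by liver iron concentration (MRI".

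For analysis, section 20.3 says "Difference between baseline versus EOT will be measured as continuous variables and analyzed with parametric or non parametric statistical tests", with the choice depending on normality. It adds "Efficacy parameters analysis will be done on FAS and PP" and defines the set as "Full Analysis Set (FAS): All enrolled patients".

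The synopsis bases the sample size on "Difference between two dependent means (matched pairs) Tail(s) = Two" at alpha 0.05, and section 20.2 names the same test. With 50 patients, power is put at almost 60% for a standardised effect of 0.30 and almost 100% for 0.50. Ten more patients are added for 20% drop-out, making 60. The objective in section 10.1 is to balance the iron burden over one year.

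**The concern.** The endpoint asks whether LIC stayed within stated limits. The planned test asks whether the average (or median) change differs from zero. These are different questions. A patient-level band depends on the spread of changes as well as their centre. A claim of stability needs an interval set against a margin, and failure to reject zero does not supply one.

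No section says how the limits enter an analysis, whether a fall below them counts as success, how the two baseline strata combine, or how a patient without an end-of-study scan is counted. If the 20.3 sentence on continuous differences belongs only to the secondary variable named just before it, the primary endpoint has no stated analysis at all.

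The trial could therefore run exactly as planned and end with no pre-stated way to say whether its primary endpoint was met. In a single-arm study with no comparator, the rule would then be chosen with the LIC results in hand.

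**Working it through.** **The plan's own figure.** Two-sided paired t test, alpha 0.05, noncentrality = dz × √n, df = n − 1. At n = 50:
- dz 0.30: noncentrality 0.30 × √50 = 2.12, power 54.8% (stated: almost 60%).
- dz 0.50: noncentrality 0.50 × √50 = 3.54, power 93.4% (stated: almost 100%).

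The stated values are looser than the exact ones. That is a separate matter, and nothing below depends on it. What matters here is that the calculation contains neither ±1.5 mg/g nor ±20%.

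**Does the test track the limits?** The documents give no SD of LIC change, so a range is assumed, with normally distributed changes.

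Baseline at most 5, mean change 0. Share in band = 2Φ(1.5/SD) − 1. The test rejects in 5% of trials by construction.

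| Assumed SD (mg/g) | 1.5/SD | Share within ±1.5 | Trials with non-significant test |
|---|---|---|---|
| 0.75 | 2.00 | 95% | 95% |
| 1 | 1.50 | 87% | 95% |
| 1.5 | 1.00 | 68% | 95% |
| 2 | 0.75 | 55% | 95% |

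Baseline above 5, mean change 0. Share in band = 2Φ(20/SD) − 1, with SD in percentage points of relative change: 95% at SD 10, 82% at SD 15, 68% at SD 20. The test is again non-significant in 95% of trials.

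**The reverse case.** Baseline at most 5, mean rise 0.5 mg/g, SD 1, so dz = 0.50.
- Share in band = Φ((1.5 − 0.5)/1) − Φ((−1.5 − 0.5)/1) = Φ(1.0) − Φ(−2.0) = 82%.
- The paired test is significant in 93% of trials at n = 50 and in 92% at n = 48 (60 × 0.8).

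So the same non-significant result goes with anything from 55% to 95% in band, and a significant rise can go with 82% in band.

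**If the limits are margins on the mean.** The relevant output is then a CI for the mean change set against ±1.5 mg/g or ±20%. None is planned. At n = 50 and a true dz of 0.30, the difference test would miss the shift in 1 − 0.548 = 45% of trials, so non-significance is weak evidence of stability.

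**Precision of an in-band proportion** (exact Clopper-Pearson 95% CI):
- 36/50 = 72%, 58% to 84%.
- 36/60 = 60%, 47% to 72%, if the ten patients without a scan count as not in band.

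The half-width is about 13 percentage points in both. The same 36 patients give 72% or 60% depending on a missing-scan rule that is not written down. This arises easily: section 16.7 schedules MRI only at baseline and end of study, and the early-withdrawal list in section 16.4 has no MRI.

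**The case against.** **The limits are nowhere called a responder definition.** True. The per-patient reading rests on their being assigned to patients by baseline LIC, on continuous change being named separately as secondary, and on the response-criteria line in the synopsis. A reader might infer that the protocol explicitly defines a responder, and it does not. But if the limits are margins on the mean, they are still unused.

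**The plan already covers categorical data.** Section 20.3 lists frequencies and percentages for categorical data and tests for nominal variables. The first is a generic descriptive line, the second concerns secondary endpoints, and neither mentions the limits. An in-band count could be reported under the first, but nothing commits the trial to it or says how to judge it.

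**The difference test is not useless.** This stands. A significant fall would support prevention of accumulation, and detecting a real mean rise is relevant. The test belongs in the plan as a secondary analysis.

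**The effect may be small in practice.** A reader might infer that the test could be non-significant while only a minority of patients stay in band. In the stratum at most 5, with mean change 0, that needs an SD of 3 or 4 mg/g (38% or 29% in band). At a baseline of 3, such an SD would put 16% to 23% of patients below zero: Φ(−3/3) and Φ(−3/4). The documents give no SD and do not support so strong a statement.

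**This is a single-arm phase II study.** A proportion with its CI and no pass/fail minimum can be acceptable, so a reader should not infer that a minimum is compulsory. Nor do the documents require unscanned patients to count as failures, which would mix iron balance with retention. Both are design choices, but they should be made in advance.

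**Conclusion.** The concern holds. The stated endpoint and the stated analysis do not match: limits of ±1.5 mg/g or ±20% define the primary endpoint, and no test, interval or sample-size statement refers to them. This follows from the text alone and does not depend on any assumed SD.

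The size does depend on assumptions. For normal changes centred on zero and SDs of 0.75 to 2 mg/g, the in-band share moves from 95% to 55% while the chance of a non-significant test stays at 95%. The per-patient reading is the natural one but is inferred. Under the alternative reading the planned p-value is equally silent on whether the limits were met. Confidence is high, and this should be settled before end-of-study LIC is analysed.

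**What to change.** In section 20.3:
1. State that the limits apply to each patient, and whether a fall below the band counts as success.
2. Make the primary analysis the proportion of patients whose LIC change lies within their own band, with an exact 95% CI, overall and by baseline stratum.
3. Report it among patients with both scans and on the FAS with unscanned patients counted as not in band. Name which one is primary before end-of-study LIC is analysed.
4. If the sponsor wants a pass/fail minimum, fix it before that analysis.
5. Keep continuous change as secondary, with its 95% CI by stratum: mg/g against ±1.5 for baseline at most 5, percent change against ±20% above 5. Say that a non-significant p-value will not be taken as evidence of balance.

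In the synopsis and section 20.2, add the precision of the in-band proportion, for example 36/50 and 36/60 with the intervals shown above, and say that the paired-t power concerns the secondary continuous change.

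The cost is a protocol amendment, which sections 23.2 and 24.7 send to the ethics committee before implementation, and a less flattering precision statement (about ±13 percentage points). If the FAS version is made primary, the proportion cannot exceed 50/60 = 83% with ten unscanned patients, or 48/60 = 80% with twelve. The bands stay as written, and no extra scans, visits or patients are needed.

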10. STUDY OBJECTIVES

10.1. Primary objective

Balance iron burden in one-year treatment in early phase of transfusion requirement by low dose (3.5 mg/kg) DFX-FCT (prevention of iron overload) as demonstrated by MRI (R2) documented hepatic iron concentration.

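### The objective is that liver iron does not accumulate, but the only LIC inference named is a test of zero change, and nothing in the plan limits a false claim of stability

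*Combined protocol and SAP*

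**What the plan says.** Section 10.1 gives the primary objective as "Balance iron burden in one-year treatment in early phase of transfusion requirement by low dose (3.5 mg/kg) DFX-FCT (prevention of iron overload"), shown by MRI-measured hepatic iron. Sections 17.2.1 and 20.3 define the primary variable as the change in LIC from baseline, with limits that depend on baseline: ±1.5 mg/g dry weight when baseline LIC is at or below 5 mg/g, and ±20% when it is above 5. Absolute change in LIC is the corresponding secondary variable. The sentence on testing comes directly after that secondary variable: "Difference between baseline versus EOT will be measured as continuous variables and analyzed with parametric or non parametric statistical tests", with the choice of test left to whether the data look normal.

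Section 20.2 sizes the trial by "using the t test Means: Difference between two dependent means (matched pairs"). The synopsis gives the settings as "Tail(s) = Two. α err prob = 0.05". Section 20.2 then states: "Including 50 subjects in the study, we can reach almost 60% power to detect small effect size 0.30 (with p value of 0.05"), and "we have almost 100% to detect moderate effect size of 0.50 (with p-value of 0.05"). It concludes that "we have enough power to detect an effect size between 0.3 and 0.5".

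The documents contain no equivalence or non-inferiority test, no confidence-interval criterion, no required proportion of patients within the limits, and no statement of what a significant or a non-significant result would mean.

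**The concern.** The result the sponsor hopes for, stable iron, is the null hypothesis of the planned test. The 5% alpha limits wrongly declaring that iron moved. Nothing limits wrongly declaring that it did not. The power in section 20.2 is the chance of detecting a change, not the chance of demonstrating stability.

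Two problems follow. Real accumulation can miss p < 0.05, and each lost or noisy scan makes that more likely. Loss of scans is a practical possibility: section 16.7 schedules MRI only at baseline and EOS, and the early-withdrawal list in 16.4 contains no MRI. In the other direction, with precise scans, a mean change well inside 1.5 mg/g can be statistically significant and appear to contradict balance. With no control arm, within-patient LIC change is the main evidence for the objective, so the rule for reading it matters.

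**Working it through.** **Inputs.** Two-sided alpha 0.05 and the paired t test (synopsis and 20.2); 50 evaluable patients, 60 enrolled with 20% drop-out (11.2, 20.2), so 60 × 0.8 = 48 completers; limit of 1.5 mg/g for baseline LIC at or below 5 (17.2.1, 20.3). The SD of LIC change is not in the documents. I assume 1.5 to 5 mg/g and show the range.

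**Method.** Power comes from the noncentral t distribution with n − 1 degrees of freedom and noncentrality dz × √n, where dz = mean change / SD of change. The probability of non-significance is 1 − power.

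**The plan's own figures (n = 50).** Power is 54.8% at dz 0.30, against almost 60% stated, and 93.4% at dz 0.50, against almost 100% stated. The stated figures are rounded upward. That is a separate, minor matter.

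**A true shift of 0.3 SD.**

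| n | Power | Non-significant |
|---|---|---|
| 50 | 54.8% | 45% |
| 48 | 53.0% | 47% |
| 30 | 35.5% | 64% |
| 20 | 24.7% | 75% |

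The rows for n = 30 and n = 20 correspond to losing 50% and 67% of 60 patients. They only illustrate losses larger than the planned 20%.

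**A true mean rise of 1.5 mg/g at n = 48.**

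| Assumed SD (mg/g) | dz | Non-significant |
|---|---|---|
| 1.5 | 1.00 | under 0.001% |
| 2 | 0.75 | 0.09% |
| 3 | 0.50 | 7.6% |
| 4 | 0.375 | 28% |
| 5 | 0.30 | 47% |

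**The opposite error.** The smallest significant mean change at n = 48 is t(0.975, 47)/√48 = 2.012/6.928 = 0.290 SD. That is 0.44 mg/g at SD 1.5 and 1.16 mg/g at SD 4, both below 1.5 mg/g. At SD 1.5, a true mean rise of only 0.5 mg/g (dz 0.333) is significant in 62% of trials.

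**A confidence-interval rule, for comparison.** Suppose success means that the upper limit of the two-sided 95% CI for mean change lies below +1.5 mg/g. With n = 48 and true change zero, it is met in 99.9% of trials at SD 2, 92% at SD 3, 72% at SD 4 and 53% at SD 5. If the true mean rise equals the margin, it is met in about 2.5% whatever the SD. More noise now makes the favourable claim harder to reach.

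**What a rule on the mean cannot show.** At n = 48 the rule is met when the observed mean lies just under 1.5 mg/g − 0.290 SD. If individual changes are normal, the share of patients above +1.5 mg/g is then 1 − Φ(0.290) = 0.386, or about 39%, at any SD.

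**The case against.** A reader might infer that the plan intends to treat p > 0.05 as proof of balance. The documents do not say so: section 20.3 gives no rule for reading either result. What can be said is that a zero-difference test offers no other route to a claim of balance.

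It can also be argued that the testing sentence governs only the secondary variable, absolute change, and that the banded primary variable would be summarised under the general provision in 20.3 for categorical data. The text allows that reading. But then the primary variable has no stated inference at all, while section 20.2 still sizes the trial on a paired difference. The limits remain attached to no threshold on either reading.

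A reader might go further and say that neither outcome of the test bears on the primary question. That is too strong. A significant rise is evidence against prevention of accumulation, and a significant fall is compatible with it. The means and SDs already planned would also let anyone compute a confidence interval.

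Finally, high miss rates for a 1.5 mg/g rise need a large SD. Below 3 mg/g they are small, and patients enter after only 5 to 20 units. This stands, which is why the whole range is shown. It limits the size of the concern, not its direction.

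**Conclusion.** The concern holds in this form: the objective is stability, the only named LIC inference is a test of zero change sized to detect change, and no rule in the plan controls the error of wrongly concluding stability. The size depends on an SD the documents do not give. At 48 completers the chance that a 1.5 mg/g mean rise goes undetected runs from negligible (SD 1.5 to 2) to nearly half (SD 5). For a shift of 0.3 SD, an effect size the plan itself uses, it is 47% at any SD. The figures assume approximately normal changes and a paired t test. The ±20% stratum was not calculated because the baseline LIC distribution is not given. How the sponsor would read a non-significant result is an inference, not a stated intention. This should be fixed before analysis. In a single-arm phase II study with a remedy that needs only wording, it does not invalidate the design.

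**What to change.** In section 20.3:

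- State that a non-significant test of zero change is not evidence of balance.
- Report mean LIC change (EOS minus baseline) with a two-sided 95% CI. Conclude prevention of accumulation on average only if the upper limit lies below a margin fixed and justified in advance for the whole cohort. The +1.5 mg/g limit applies to individual patients with baseline LIC at or below 5, so it can be a reference but should not be adopted as the cohort margin unexamined.
- Alongside this, report the proportion of patients within their own limit (±1.5 mg/g or ±20% by baseline) with a 95% CI, because the mean alone can satisfy the rule with over a third of patients above +1.5.
- Say explicitly which analysis belongs to the primary variable and which to the secondary.

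In section 20.2, replace the power statement with the probability of meeting the chosen rule at 48 to 50 evaluable patients over a range of SDs.

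The cost is protocol and SAP wording and one recalculation, with no added patients or procedures. The downside is that the claim is harder to reach if LIC change proves very variable.

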11.2. Number of patients

A total of 60 patients will be enrolled in the study: 50 +10 for a planned 20% drop out rate (drop out rate estimated on others DFX DT – MDS prospective studies).

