11.3. Duration of the study

Patients will be recruited over 12 months and followed for 1 year treatment phase. The anticipated study dates (start / end) are:

- Total accrual period (months/years): 12 months
- The duration of the treatment period is 12 months
- End of the study: last patient last visit.
- The Final Study Report will be provided after the end of the Study.

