17.2.2. Secondary objective and endpoints

	Secondary Objectives	Secondary Endpoints
Descriptive-observational objective	Definition of iron overload (including serological markers and MRI definition of iron loading in different tissues: liver, pancreas), tissue reactive iron species and oxidative stress in MDS at beginning of transfusional history.	Absolute values of serum ferritin, transferrin saturation, NTBI, LPI, liver and pancreas MRI and oxidative stress at baseline.
	Efficacy	Absolute change in hepatic iron concentration EOS versus baseline.
	On year evolution of iron overload serologic markers	Absolute and relative changes in serum ferritin and transferrin

		saturation from baseline to every visit during the whole treatment period.
	Presence and quantitative evolution of toxic serum iron forms (iron tissue reactive species) under low dose DFX therapy.	Proportion of patients with NTBI > normal values and/or LPI > normal values at end of study vs baseline. Changes in NTBI and LPI from baseline to every visit during the whole treatment period.
	Verify if regular suppression of the “free iron forms” prevent accumulation of tissue iron.	Relationship between NTBI and LPI with serum ferritin and liver and pancreas iron overload (MRI) at end of study versus baseline
	Evaluate the overall safety of deferasirox FCT formulation in patients with lower risk MDS at the beginning of their transfusional history	Overall safety, as measured by frequency and severity of reported AEs and SAEs and changes in laboratory values from baseline: serum creatinine, creatinine clearance ALT, AST, complete blood count (platelets, RBC and WBC) and total direct and indirect bilirubin).
	Leukemic transformation (progression to leukemia or higher rIPSS scores)	Proportion of patients with a disease progression (progression defined as a transition into a higher MDS risk group based on revised IPSS scoring or progression to AML) Time to progression (defined as above) or to leukemia transformation.

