	Hemopoietic response	Percentage of patients with hematologic improvements in term of erythroid response following IWG 2006 criteria. Time to reach transfusion dependence defined as > 2 PRBC units/months for 3 months for patients with pre-transfusional Hb < 9.0 g/dl (or <10 g/dl for patients with cardiac disease) or a total number of PRBC units received = 20 from baseline. Absolute reticulocytes count from baseline to every visit during the whole treatment period. Absolute values and evolution of serum transferrin receptor, GDF11, GDF 15 and erythroferrone from baseline to every visit during the whole treatment period. Evaluation of transfusional ratio: number of units received in a

		predetermined period/ Mean pre-transfusional Hb level. Compared with other studies on general population (study and FISIM-ETS registry). Patients receiving concurrent rHuEpo will not be considered for erythroid response
	Costs analysis	Cost and outcome with low dose in early chelation vs. chelation treatment in MDS patients with transfusional iron overload in accordance with either local or international guidelines
Exploratory objective and endpoint	Study of biological cellular damage by iron toxicity before and during treatment	MDA values during the study and relationship to NTBI and LPI values

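### The blanket rule for secondary endpoints does not fit the two time-to-event endpoints, which need a method that handles censoring and death

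*Combined protocol and SAP*

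**What the plan says.** Section 17.2.2 lists two secondary endpoints that are times to an event: "Time to progression (defined as above) or to leukemia transformation" and "Time to reach transfusion dependence defined as > 2 PRBC units/months for 3 months" (the latter with an alternative limb based on the total number of units received). Beside the first it lists a proportion: "Proportion of patients with a disease progression (progression defined as a transition into a higher MDS risk group", or progression to AML. Death without progression is not part of that definition.

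Section 20.3 covers every secondary endpoint with one sentence: "secondary endpoints will be evaluated as continuous or nominal variables and analyzed accordingly with parametric or non parametric tests". The summaries it offers are "Frequencies and percentages for categorical data" and "n, mean, standard deviation, minimum, median, 25th and 75th percentiles and maximum for continuous data". Efficacy parameters are analysed on both the Full Analysis Set (all enrolled patients) and the Per Protocol set (no major violation, and either completed treatment or withdrew for unsatisfactory therapeutic effect).

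The documents expect incomplete follow-up. Patients are "followed for 1 year treatment phase" (11.3), with a "planned 20% drop out rate" (11.2). Section 15.1 lists death and loss to follow-up among the reasons for stopping treatment. Under 15.2, nothing further is collected on a patient who withdraws consent to further data. No section names a Kaplan-Meier or cumulative incidence estimate, a censoring rule, a time origin for progression, or a treatment of death for these endpoints. PFS and OS appear only in the abbreviation list.

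**The concern.** A right-censored time is neither a continuous nor a nominal variable. If it is summarised as continuous, the analyst must either use only patients who had the event or mix event times with censoring times. Both summaries are bounded by 12 months whatever the disease does. If the endpoint is reduced to a percentage, patients who left early must be counted as event-free or removed, and each choice biases the result in its own direction. Death before the event has no rule at all.

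At stake is whether the reported times and proportions for progression and transfusion dependence can be interpreted. In an open-label trial, leaving the method open also means that it may be chosen after the data have been seen.

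**Working it through.** The plan gives no event rate, median or event count for these endpoints, so there is no figure of its own to reproduce. What follows is illustration.

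**Inputs from the documents:** 12 months of follow-up (11.3); 20% drop-out (11.2, 20.2); Full Analysis Set of all enrolled patients, and Per Protocol set mainly of completers (20.3).

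**Assumed:** constant event hazard, independent constant drop-out hazard, no deaths at first, and a true 12-month risk p from 10% to 50%.

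**Formulas.** Let a = −ln(1 − p), c = −ln(1 − 0.20) = 0.2231 and T = a + c. The fraction of patients followed for 12 months without an event is E = (1 − p) × 0.80.

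- Crude proportion in the Full Analysis Set: F = (a/T)(1 − E)
- Events over events plus completers: F/(F + E)
- Mean time among events: 12/T − 12E/(1 − E) months
- Mean of all observed times: 12(1 − E)/T months
- True median: 12 ln 2/a months

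**Worked case, p = 40%.** a = 0.5108, T = 0.7340, E = 0.60 × 0.80 = 0.48.

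- F = (0.5108/0.7340) × 0.52 = 36.2%
- 0.362/(0.362 + 0.48) = 43.0%
- Mean among events = 16.35 − 11.08 = 5.3 months

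**Worked case, p = 15%.** a = 0.1625, T = 0.3857, E = 0.68.

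- F = (0.1625/0.3857) × 0.32 = 13.5%
- 0.135/(0.135 + 0.68) = 16.5%
- Mean among events = 31.12 − 25.50 = 5.6 months

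| True 12-month risk | Crude, all enrolled | Events/(events + completers) | Mean time among events (months) | Mean of all observed times (months) | True median (months) |
|---|---|---|---|---|---|
| 10% | 9.0% | 11.1% | 5.7 | 10.2 | 79 |
| 15% | 13.5% | 16.5% | 5.6 | 10.0 | 51 |
| 20% | 18.0% | 22.0% | 5.6 | 9.7 | 37 |
| 30% | 27.1% | 32.6% | 5.4 | 9.1 | 23 |
| 40% | 36.2% | 43.0% | 5.3 | 8.5 | 16 |
| 50% | 45.4% | 53.2% | 5.1 | 7.9 | 12 |

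The mean among events moves by only 0.6 months while the true median moves from 12 to 79 months. The crude proportion is low by 1.0 to 4.6 points, and the completer-based one is high by 1.1 to 3.2 points.

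The completer-based ratio stands in for the Per Protocol set only if patients with an event stay in that set. For transfusion dependence this is partly built in: the set keeps withdrawals for unsatisfactory effect, which 15.1 ties to a heavy transfusion burden. For progression it is less certain.

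**Adding deaths.** Take p = 40% as the risk in the absence of death, and add 10% deaths (assumed; d = 0.1054).

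- Cumulative incidence: (0.5108/0.6162) × (1 − 0.60 × 0.90) = 0.829 × 0.46 = 38.1%
- Crude proportion, all enrolled: (0.5108/0.8393) × (1 − 0.60 × 0.80 × 0.90) = 0.6086 × 0.568 = 34.6%
- One minus Kaplan-Meier with death censored: 40%, which overstates the 38.1%

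**The case against.** The sentence in 20.3 is generic. It does not say that times will be averaged among patients with events, or that drop-outs will count as event-free. A reader might infer that the plan has decided to ignore censoring and death, but the text does not say so. Non-parametric tests could loosely include Kaplan-Meier methods. This stands as a limit on the wording. It does not rescue the rule, because the variable types and the listed summaries leave no place for a censored time.

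A reader might also infer that all reported proportions would be too low. That holds for the Full Analysis Set only; the Per Protocol set drops most non-completers and tends the other way.

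The figures need care. Every event rate is assumed. The bias in proportions is below one standard error at n = 60: at 36.2%, √(0.362 × 0.638/60) = 6.2 points against a bias of 3.8; at 13.5%, 4.4 points against 1.5. In the 40% case the true median of about 16 months lies beyond follow-up, so Kaplan-Meier would not recover it either. The contrast with 5.3 months shows that the mean is uninformative, not that a better estimator would deliver the median.

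A constant hazard also fits transfusion dependence poorly. Its rate limb needs three months of transfusions, and patients enter below that rate. Nor is drop-out independent of the event: patients stopped under 15.1 for transfusion burden have already exceeded the endpoint's rate, so they are events and should not be censored.

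**Conclusion.** The concern holds as a mismatch between method and endpoint. A single stated rule covers all secondary endpoints, two of them are right-censored with death possible, and nothing elsewhere supplies a suitable method. The failure is serious for the times, which would reflect mainly the 12-month cut-off. It is modest for the proportions: about 1 to 5 points low among all enrolled patients and about 1 to 3 points high on a completer basis, under constant hazards, independent 20% drop-out, no deaths and risks of 10% to 50%.

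These sizes are illustrative, because the documents give neither event nor death rates. Both endpoints are secondary, in a single-arm study whose sample size was not based on them. The primary hepatic iron analysis is unaffected, and nothing here supports a wider criticism of it. The change should be made before analysis, but it does not threaten the trial.

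**What to change.** In 20.3, exempt the two endpoints from the continuous-or-nominal rule and state that:

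- time runs from first dose;
- both are estimated by cumulative incidence (Aalen-Johansen), with death without the event as a competing event;
- event-free patients are censored at the last assessment at which that endpoint could be evaluated;
- patients who met the endpoint definition before discontinuation count as events;
- the 12-month cumulative incidence is reported with a 95% confidence interval, plus a 6-month estimate for transfusion dependence, in place of mean times;
- the protocol-defined crude proportion with progression is kept as a descriptive figure beside it.

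A 6-month estimate for progression is not advised. The only on-treatment marrow assessment marked in the 16.6 schedule is at end of study, and 16.3 asks for it only if clinically indicated.

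The cost is a short paragraph and slightly more analysis work, with no added patients or visits. The timing of progression will stay imprecise because of the marrow schedule, and the report should say so.
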